The arguments in favor of virtual triage in the ED are much stronger. We expect that this change will reduce risk to patients, and risk to others, from violent outbursts. We expect that both phases will reduce patient discomfort, distress, and fear. Lessening decompensation by patients in the ED will allow therapeutic strategies to commence earlier, contributing to earlier recovery and earlier hospital discharge.

It is worth noting that our project is defensible on the basis of benefit to patients alone (otherwise, we would not consider it). There are other likely benefits, which do not enter directly into our calculus. This project is likely to reduce ED crowding. Also, this project will save the attending psychiatrist the need to travel to the hospital for most evaluations. We emphatically repeat that while these are indeed benefits, they are not the basis for us performing the study, nor would they be a sufficient reason for this change in policy.

2. Objectives

- i. We will implement tele-psychiatry evaluations in the ED.
- ii. We will evaluate the impact of this strategy on patient outcomes and healthcare utilization, compared to historical controls.

3. Working Hypotheses

- a. Remote video psychiatric examination is safe and effective, as measured by clinical outcomes, when compared to usual practice. Patients will spend fewer minutes in the ED, compared with historical controls. There will be fewer violent incidents in the ED. There will not be an increase in the frequency of reversal of involuntary hospitalization, which would imply that a patient was needlessly admitted.
- b. Implementation of telepsychiatry will be feasible within the current context, infrastructure, and resources.

4. Comprehensive description of study design and methodology:

Patient Population

We will recruit study participants from the Jerusalem Mental Health Center, located at Kfar Shaul and Ichilov Medical Center. We will obtain a waiver of informed consent, as this will be a change in standard procedure for all patients for the duration of the study.

We will include all patients who require an ED interview and an involuntary admission decision by a senior psychiatrist. We will compare patients from the three months prior to the study (approximately 60, based on usual rates of admissions) with patients from the three months of the study (also 60).

The absence of exclusion criteria will ensure that the study results will be broadly generalizable.

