Independent Variables (The Intervention)

In each study phase, the independent variable will be the study intervention, which will be organized by time. Patients in the pre-intervention period (3 months) will be managed under usual care, and will be the comparison group. Patients in the post-intervention period (3 months) will be managed using the study intervention, and will be the “intervention” group.

Usual care is that patients with psychiatric emergencies are evaluated face-to-face in the ED by a senior psychiatrist for possible involuntary admission. The intervention is that this evaluation will take place via video-link.

Dependent Variables

Dependent Variables

Variable	Type	Data Collection Method
Interobserver Variability	Binary	All video interviews will be recorded. A second senior psychiatrist, blinded to the admission decision, will determine whether admission was warranted based on the recording.
Reversal of Admission	Binary	An involuntary admission which is reversed within 24 hours implies an unnecessary admission. The proportion of admissions reversed within 24 hours will be measured.
Emergency Room Length of Stay	Continuous (minutes)	Measured from the time of arrival in the ED until the patient physically leaves the ED – to go home or to go to the psychiatry ward. Already collected as part of routine practice.
Time from ED arrival to assessment	Continuous (minutes)	We will measure this ourselves, starting with the pre-intervention period. We will measure time until the senior psychiatrist begins his/her face-to-face or virtual assessment.
Violent Incidents in the ED	Binary (any/none)	As recorded by ED staff and adjudicated by blinded review of the chart by a senior psychiatrist.
Patient satisfaction with ED course	Ordinal	We will ask patients to rate their overall satisfaction with their stay in the ED, from 1-5 (very dissatisfied – very satisfied), as they are leaving – starting with the pre-intervention period.
Staff satisfaction with ED flow	Ordinal	We will ask physicians, nurses, and other staff to rate their overall assessment of ED flow, from 1-5, at the end of each month
Duration of hospitalization	Continuous	From the time of entering the ward until the time of leaving the hospital, in hours

Statistical Analyses

We will be comparing the pre-intervention period with the post-intervention period. Above, we have outlined the dependent variables for each phase, and how we will collect them.

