We will start by comparing the pre- and post-groups on important baseline characteristics. These will include age, sex, ethnic/social group (Haredi, Arab, General Population), socioeconomic status, and underlying condition (schizophrenia, bipolar disorder, other). We will compare these variables between pre- and post-groups using appropriate bivariate tests (t-test, chi-square). If we find a statistically significant imbalance ($p < 0.05$), we will utilize a multivariable analysis in the main analysis to correct for the imbalanced factors. We do not propose to control for all potential covariates because of limited sample size.

In the main analysis, we will compare the dependent variables explained above between the pre- and post-periods. For continuous variables, we will use an unpaired t-test. For categorical variables, we will use a chi-square test. We will perform two-tailed tests, and will consider $p < 0.05$ to be statistically significant. In the event that we have detected an important between-group imbalance, we will use an appropriate regression model (logistic or generalized linear model), controlling for only the factors that have been found to be unbalanced.

Potential Sources of Bias

A sample size of 60 each in the pre- and post-intervention groups will make it unlikely, but not impossible, that random chance will lead to important between-group imbalance on measured factors. We will assess for such imbalance as part of the analysis plan, as noted above. If there are important differences, we will conduct multivariable analyses to control for a limited number of important unbalanced covariates.

Justification of Sample Size and Study Duration

The study duration is dictated by the maximal duration of a study funded by Machon HaLeumi. The sample size is dictated by the approximate number of patients admitted to our center each month. With 60 patients in the pre-intervention period and 60 in the post-intervention period, we will have statistical power to show a large effect size for some variables, and a moderate effect size for others. For example, if we assume that the average time in the ED is currently

3 ± 1 hours, and that the Phase 1 intervention will reduce this time by one hour, with 60 patients in each group, we would have 80% power to detect such a difference.

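### The ED-only violence outcome answers the ED hypothesis but cannot support the broader claim of reduced violence, because the intervention is expected to shorten the time over which violence is observed

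*Combined protocol and SAP*

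**What the plan says.** - **Hypothesis (section 3, Working Hypotheses).** "There will be fewer violent incidents in the ED". The same paragraph predicts the shorter stay: "Patients will spend fewer minutes in the ED, compared with historical controls".
- **Outcome (section 4, Dependent Variables table).** Violent incidents in the ED are scored any or none per patient, "As recorded by ED staff and adjudicated by blinded review of the chart by a senior psychiatrist". No ward or post-ED source is named.
- **Observation window (same table).** ED length of stay is "Measured from the time of arrival in the ED until the patient physically leaves the ED", so the period in which violence can be counted is itself a study outcome.
- **Analysis (Statistical Analyses).** Categorical outcomes are compared by chi-square. The regression fallback adjusts only for baseline factors found to be unbalanced. There is no time-at-risk denominator and no fixed window from arrival.
- **Size of the shortening (Justification of Sample Size and Study Duration).** As an example for power, ED time is taken as "3 ± 1 hours, and that the Phase 1 intervention will reduce this time by one hour".
- **Wider claim (section 1c, Conceptual Framework and Ethical Analysis).** "We expect that this change will reduce risk to patients, and risk to others, from violent outbursts". Section 5 (Significance) predicts less violence and shorter hospital stays without limiting the violence to the ED.

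**The concern.** Acute agitation need not end when the patient leaves the ED. Suppose an admitted patient would have become violent in the third hour after arrival. Under usual care the patient is still in the ED and the incident counts. If video assessment moves the patient to the ward after two hours, the same incident happens on the ward and no listed outcome records it. The two periods are then compared over different lengths of the same acute episode, and relocation looks the same as prevention.

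For a shorter stay, this effect can only favour video. What is at stake is the step from a lower ED count to a statement that patients and those around them are safer, which section 5 hopes will inform Ministry of Health policy.

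**Working it through.** **The plan's own figure.** The documents give no baseline rate, effect size or power for violence. Their only power figure is 80% for ED time. With 60 per group, a difference of 1 h and an SD of 1 h, power is Φ(1/√(2/60) − 1.96) = Φ(5.48 − 1.96) ≈ 99.98%, so the 80% is not reproduced. That is a separate matter and does not affect this point.

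**Inputs.**
- From the plan: ED time of 3 h falling to 2 h (the power example), 60 per group, two-sided 0.05.
- Assumed: baseline proportion p with an ED incident of 5%, 10%, 20% or 30%, and the shape of the risk over time.
- In every case the patient's risk at a given time since arrival is the same in both periods and does not depend on place. The true effect on violence is therefore nil.

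**Formula.** If a fraction f of the three-hour cumulative hazard falls in the first two hours, the ED-only proportion after shortening is p₂ = 1 − (1 − p)^f.
- Constant hazard: f = 2/3 = 0.667.
- Hazard halving every hour: f = (1 − 1/4)/(1 − 1/8) = 0.857.
- Hazard halving every 30 minutes: f = (1 − 1/16)/(1 − 1/64) = 0.952.

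| Baseline p | Constant hazard | Halving every hour | Halving every 30 min |
|---|---|---|---|
| 5% | 3.4% (−32.8%) | 4.3% (−14.0%) | 4.8% (−4.7%) |
| 10% | 6.8% (−32.2%) | 8.6% (−13.7%) | 9.5% (−4.5%) |
| 20% | 13.8% (−30.9%) | 17.4% (−13.0%) | 19.1% (−4.3%) |
| 30% | 21.2% (−29.5%) | 26.3% (−12.2%) | 28.8% (−4.0%) |

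Relative falls are in brackets. Letting stays vary (gamma, SD 1 h) barely changes the constant-hazard result: 20% becomes 13.7%. A hazard that rose with time since arrival would give f below 2/3 and a larger fall, so the table is an illustration and not a bound. With one common window in both periods, every row gives a risk ratio of 1.00.

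**Inferential weight.** Under constant hazard the expected numbers of patients with an incident, out of 60, go from 3.0 to 2.0 (5% baseline), 12.0 to 8.3 (20%) and 18.0 to 12.7 (30%). The chance that this alone gives p < 0.05 in favour of video is Φ[(p − p₂ − 1.96·SE₀)/SE₁], with SE₀ pooled and SE₁ unpooled. That is about 6%, 14% and 20% (approximate at the smallest counts).

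**Would a common window detect a calmer ward?** Take a 20% baseline and constant ED hazard h = −ln(0.8)/3 = 0.0744 per hour.
- Ward hazard zero, 24 h window: 20% v 13.8%, power about 15%.
- Ward hazard h/2, 24 h window: cumulative hazard 3h + 10.5h = 13.5h v 2h + 11h = 13h, so 63.4% v 62.0%, a difference of 1.4 points.
- Ward hazard h/2, 6 h window (for comparison only): 4.5h v 4h, so 28.4% v 25.7%, a difference of 2.7 points.

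A long window is dominated by ward time that both periods share. A shorter one dilutes less, but precision stays low: at 20% in both groups the 95% interval for the difference is about ±1.96·√(2 × 0.2 × 0.8/60) = ±14 points.

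**The case against.** The strongest reply is that less exposure to the ED is the plan's stated mechanism and not an artefact. The hypothesis is worded for the ED, the outcome measures exactly that, and sections 1a and 1c argue that waiting in the ED creates opportunities to decompensate and that patients are often calmer on the ward. **This stands for the ED hypothesis.** A reader might infer that the ED-only outcome is invalid and should be replaced. The documents do not support that: a fall in ED violence through shorter stays is a real answer to the question asked.

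It can also be said that the section 1c sentence on risk sits in a discussion of ED triage and may be meant for the ED. That is a fair reading of that sentence, but section 5 carries no such limit. The view that the ward is calmer rests on experience and is not tested by any listed outcome.

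A reader might also infer that the plan commits to a one-hour cut and so to a spurious fall of about a third. It does not. The one-hour figure is a worked example for power, and only the direction is hypothesised. The one-third figure further needs a constant hazard that is equal in ED and ward, which the documents do not establish and which their remark about calmer wards argues against.

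Finally, the plan concedes that some outcomes will not be definitive and describes a relatively small feasibility study. That limits the harm but does not tell a reader what a lower ED count means.

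**Conclusion.** The concern holds in a limited form. The ED-only outcome is adequate for violence in the ED. It cannot separate prevention from relocation to the ward, so it does not support a claim of lower overall risk from violence. The possible size runs from about 4% to 33% in relative terms over the hazard shapes and the 5% to 30% baselines examined. All of these are assumptions, since the documents give no rate or time course, and the effect disappears if ED stays do not shorten.

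A reader might go further and infer that the trial will falsely declare success on violence. The numbers do not show that: even under constant hazard, this mechanism alone reaches significance in roughly 6% to 20% of such studies. The realistic risk is a numerical fall being read as a safety benefit. Nor would a 24-hour count reliably reveal a calming effect of the ward, so substituting it for the ED outcome is not a clear gain.

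**What to change.** 1. Keep the ED-only outcome for the ED hypothesis, and limit conclusions from it to violence in the ED.
2. Add a prespecified outcome: any violent incident, in the ED or on the ward, within a fixed time from ED arrival, with the same definition and the existing blinded chart adjudication in both periods.
3. Have the sponsor set the window in advance. It should cover nearly all ED stays in both periods without being dominated by shared ward time; 24 hours would dilute the contrast.
4. Rest any claim of reduced overall violence on the common-window result with its confidence interval, and do not read non-significance as evidence of no effect. Align the wording of sections 1c and 5 with this.
5. Report the common-window outcome among admitted patients as well, because capture is incomplete for those sent home and a change in the proportion admitted would change coverage.

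**Cost.** The reviewer reads early ward notes as well as the ED chart for about 120 patients; no new data source is needed. Limits to state: ED and ward staff may record incidents differently, violence at home is largely unseen, and precision is low.

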5. **Significance:** This innovative approach, supported by the results of our previous research,⁷ has not been tried before. We have not found any research reports assessing the impact of such a strategy, nor are we aware of this approach being used in practice inside or outside Israel. Our proposed study has the potential to lead to a system of care that is quite different from current practice, and could improve patient safety and well-being by preventing long waits and thus opportunities for decompensation. We expect to show that this approach allows patients to be put in a safer place much faster, and spend less time in uncontrolled settings. We hypothesize that this will be expressed in fewer violent incidents and shorter hospital stays.

If our study proves that a remote psychiatric examination is feasible, safe and effective, this approach may be incorporated into official policy by the Ministry of Health. Patients would be able to have an expert, accurate, reliable and fast psychiatrist examination. This approach also has great potential to help patients, and health systems, located far from psychiatric specialists. In the Israeli periphery, patients may wait even longer to be assessed than patients who live near population centers, with an even higher risk of decompensation. With a tele-psychiatry approach, a similar level of care could be provided to anyone, regardless of their location.

6. Resources available to the investigators:

[name] is an expert in health services research, implementation science, and medical outcomes research. [name] is an expert in psychiatry and telepsychiatry, who has contacts in the world of Israeli psychiatry and with the MOH. They are thus well-suited to co-lead this investigation. [name] was lead author on our previous study about the validity and reliability of telepsychiatry;⁷ the present study will continue his involvement with this line of research. [name] is the manager of inpatient psychiatry at Kfar Shaul, and will oversee day-to-day study operations. The team has the necessary connections with day-to-day operations at Kfar Shaul to ensure that the data will be collected continuously, and the necessary expertise to conduct the study.

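### Wrong decisions to send a patient home have no before/after outcome: the only comparable measure of decision error counts needless admissions

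*Combined protocol and SAP*

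**What the plan says.** Section 3 (Working Hypotheses) states that remote examination is safe and effective compared with usual practice, and spells this out in three ways: less time in the ED, less violence ("There will be fewer violent incidents in the ED"), and no rise in reversals ("There will not be an increase in the frequency of reversal of involuntary hospitalization, which would imply that a patient was needlessly admitted").

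In section 4, Patient Population takes in everyone who needs an involuntary-admission decision, so it includes people who are then sent home. The Dependent Variables table defines the relevant measures:

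- Reversal of Admission: "An involuntary admission which is reversed within 24 hours implies an unnecessary admission". Its denominator is admissions: "The proportion of admissions reversed within 24 hours will be measured".
- Violent Incidents in the ED: "As recorded by ED staff and adjudicated by blinded review of the chart by a senior psychiatrist".
- Interobserver Variability: video interviews are recorded, and "A second senior psychiatrist, blinded to the admission decision, will determine whether admission was warranted based on the recording".

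Statistical Analyses compares the dependent variables between the two periods. Section 5 (Significance) looks ahead to adoption as national policy: "If our study proves that a remote psychiatric examination is feasible, safe and effective".

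**The concern.** An admission decision can fail by admitting someone who did not need it or by releasing someone who did. The protocol's own background describes these patients as possibly dangerous to themselves or others, so the second error is not a minor one. Yet the plan compares only the first between periods.

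If video assessment led psychiatrists to release more patients, some of them wrongly, the before/after comparison has no outcome designed to show it. The study could then support a statement that video is safe relative to usual practice, and a policy built on that statement, without comparative evidence on this error.

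**Working it through.** **The plan's own figures.** There are none to reproduce on this point. The documents give no admission proportion, reversal rate or rate of harm after release. The one power statement concerns ED time and has no bearing here.

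**Step 1: what each listed outcome can show about a wrong release.**

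| Outcome (Dependent Variables table) | Comparable before/after? | Could it register a wrong release? |
|---|---|---|
| Interobserver variability | No; only video interviews are stated to be recorded | Yes, in video patients, as a disagreement |
| Reversal of admission | Yes | No; admitted patients only |
| ED length of stay | Yes | No; the clock stops when the patient leaves |
| Time from arrival to assessment | Yes | No; it ends before the decision |
| Violent incidents in the ED | Yes | No; leaving ends the exposure |
| Patient satisfaction | Yes | No; asked on leaving |
| Staff satisfaction | Yes | No; monthly rating of ED flow |
| Duration of hospitalization | Yes | No; needs an admission |

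No row is both comparable between periods and able to register a wrong release. The proportion admitted is not a row at all.

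**Step 2: can more releases lower the reversal proportion?** Assumed counts: 60 evaluated per period; 40 admitted before, 3 of them reversed. Reversal proportion = reversals / admissions.

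- Before: 3/40 = 7.5%.
- Video releases 4 patients who all needed admission, none of whom would have been reversed: 3/(40 − 4) = 3/36 = 8.3%. The proportion rises slightly.
- Video releases 6 borderline patients, 4 needing admission and 2 who would have been reversed: (3 − 2)/(40 − 6) = 1/34 = 2.9%. The proportion falls.

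A second assumed set starts from 5/45 = 11.1% and releases 6 patients. If 3 of them would have been reversed, the result is 2/39 = 5.1%; if only 1, it is 4/39 = 10.3%.

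The reversal proportion therefore falls only when the released group contains would-be reversals at a higher rate than the admitted group as a whole. When it does fall, the wrongly released patients in the same group leave no trace in it.

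**Step 3: would the fall be declared a benefit?** Uncorrected chi-square for 3/40 against 1/34: 74 × (3×33 − 37×1)² / (40 × 34 × 4 × 70) = 284,456 / 380,800 = 0.75, p ≈ 0.39. It would not reach the plan's 0.05. It would, however, agree with a hypothesis that asks only for no increase.

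**Step 4: what the added outcomes could deliver.**

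- Proportion admitted, same example: 40/60 = 66.7% against 34/60 = 56.7%, a difference of −10.0 points. Standard error = √(0.667×0.333/60 + 0.567×0.433/60) = 0.088, so the 95% interval is about −27 to +7 points.
- No events in 20 released patients: exact two-sided 95% upper limit = 1 − 0.025^(1/20) = 16.8%. For 10 and 30 patients it is 30.8% and 11.6%.
- Post-release event in 5% against 15% of all 60 per period (assumed rates): power = Φ[(0.10√60 − 1.96√(2×0.10×0.90)) / √(0.05×0.95 + 0.15×0.85)] = Φ(−0.14) = 45%. About 141 per period would be needed for 80%.

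These outcomes would put the missing error on the record. They would not exclude it.

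**The case against.** Several things count against a stronger reading, and most of them stand.

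- A reader might infer that safety is judged only through needless admissions. It is not: violence in the ED is a stated hypothesis and a before/after outcome with blinded adjudication. It measures harm during the stay, though, not whether the decision was right.
- A reader might infer that wrong releases would go undetected. The second reader sees all video interviews, not just those of admitted patients, and could disagree with a release. That stands. What is missing is a face-to-face comparator, information beyond the recording, an analysis by direction of disagreement, and any mention in the hypotheses.
- A reader might infer that releasing dangerous patients would improve the reversal outcome. Releasing only patients who needed admission would raise it (8.3% against 7.5% above). A fall requires would-be reversals among those released.
- The group's 38-patient study (section 1b) reports kappas of 0.81 to 0.95 across rater pairs, including face-to-face against video, for disposition and involuntary admission. Section 1c keeps in-person evaluation for cases of doubt. Both reduce the concern. Agreement in 38 patients does not show the direction of disagreements or what happened after release, and a confident wrong release would not trigger the in-person option.
- The section on sample size concedes that some findings on harm will not be definitive, and the policy sentence in section 5 is conditional. That tempers the claim, but it does not supply an outcome.

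**Conclusion.** The concern holds in this form: the only before/after measure of decision error looks at needless admission, nothing follows patients who are sent home, and the single measure able to show a wrong release is confined to video patients. As written, the plan cannot support a comparative claim that video is safe with respect to wrong release.

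The documents do not show that wrong releases will increase, that they would be invisible, or that they would be scored as success. The size of any effect is unknown. The worked counts are assumptions, and so is the number sent home: the figure of 60 is tied to usual admission rates, so it may not describe everyone evaluated. The conclusion about the missing outcome follows from the outcome definitions and does not depend on those counts.

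**What to change.** 1. Add the proportion involuntarily admitted as an outcome in each period, with all evaluated patients as denominator.
2. Report second-reader disagreements by direction: reader would admit but patient released, and the reverse. This uses data already planned.
3. Add one routine-records outcome, defined identically in both periods: not admitted at the index visit, followed by an ED return, a psychiatric admission, or recorded self-harm or violence within a fixed window (for example 30 days). Use all evaluated patients as denominator, and give the counts among those released alongside.
4. Report risk differences with 95% intervals for items 1 and 3, and do not read a non-significant difference as evidence of safety.

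The cost is one amendment and a records look-up for about 120 patients, with no new procedure or assessor. The data use under the consent waiver must cover the look-up. Events treated elsewhere will be missed, and the intervals will be wide. If item 3 is not collected, the safety conclusion should be limited to needless admission and events in the ED, which costs almost nothing.

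### The plan does not say whether the unit is the person or the visit, and its unpaired tests make no allowance for repeat attenders, so the 5% error rate is not assured in either direction

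*Combined protocol and SAP*

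**What the plan says.** Under Patient Population (section 4) the inclusion rule is "We will include all patients who require an ED interview and an involuntary admission decision by a senior psychiatrist". The protocol adds that "The absence of exclusion criteria will ensure that the study results will be broadly generalizable". The three months before the study are compared with the three months of the study. The number in each period is "approximately 60, based on usual rates of admissions", and the sample-size section says "The sample size is dictated by the approximate number of patients admitted to our center each month".

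The Dependent Variables table defines the main outcomes per episode. ED length of stay runs from one arrival to one departure. Time to assessment and violence relate to one ED stay. Reversal is a proportion of admissions, and duration of hospitalization covers one stay.

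Statistical Analyses (section 4) then states "For continuous variables, we will use an unpaired t-test" and "For categorical variables, we will use a chi-square test", with "We will perform two-tailed tests, and will consider $p < 0.05$ to be statistically significant". If a baseline imbalance is found, "we will use an appropriate regression model (logistic or generalized linear model), controlling for only the factors that have been found to be unbalanced". Neither the main tests nor this fallback has a term for the person. No rule covers someone who qualifies twice within a period, or once in each.

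**The concern.** Both named tests take every record to be independent of every other. The periods adjoin, nobody is excluded, and schizophrenia and bipolar disorder are the two conditions named for the baseline comparison. Some people may therefore qualify more than once, although the documents do not say how many.

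The gap matters on either reading of the unit:

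- **If visits are counted,** several visits by one person in a period carry less information than the same number of separate people. The test then understates the standard error.
- **If persons are counted,** someone seen in both periods contributes positively correlated values to the two sides of the comparison. The unpaired test then overstates the standard error. The plan also does not say which of several visits supplies the data, so that choice is left open until outcomes are known.

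At stake is the meaning of p < 0.05 for every patient-level comparison between the periods.

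**Working it through.** **The plan's own figure.** The sample-size section gives 60 per group, a difference of 1 h and ± 1 h (read as an SD), with 80% power. Power = Φ(1/√(2/60) − 1.96) = Φ(5.48 − 1.96) = 99.98%, so the 80% does not reproduce. What 60 per group detects with 80% power is (1.96 + 0.84) × √(2/60) ≈ 0.51 SD. That mismatch is a separate matter. The 0.51 SD effect is used below only to price the fix.

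**Inputs.** From the documents: 60 records per period, two-sided 5%, tests that assume independence. Assumed, because the documents give nothing:

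- within-person correlation ρ of 0.3 to 0.7;
- 60 visits coming from 50 people (10 with two visits, 40 with one) or from 46 people (4 with three, 6 with two, 36 with one);
- either no one, or 20% of people, in both periods.

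**Formula.** Let person i contribute aᵢ visits before and bᵢ after. Relative to independent records, the variance of the difference in means is multiplied by

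V = 1 + ρ × [(Σa² + Σb²)/120 − 1 − Σab/60],

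and the actual error rate is 2 × (1 − Φ(1.96/√V)). The same V applies approximately to proportions, with ρ the correlation of the binary outcome.

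**No overlap between periods**

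- 50 people: Σa² = 10×4 + 40 = 80 and 80/60 − 1 = 0.333. V = 1.10 to 1.23; error rate 6.2% to 7.8%.
- 46 people: Σa² = 4×9 + 6×4 + 36 = 96 and 96/60 − 1 = 0.60. V = 1.18 to 1.42; error rate 7.1% to 10.0%.

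**20% of people in both periods**

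| People per period | Who overlaps | Σab | Bracket | V | Error rate |
|---|---|---|---|---|---|
| 50 | 10 single-visit people | 10 | 0.333 − 0.167 = 0.167 | 1.05–1.12 | 5.6–6.4% |
| 50 | 10 at random (mean 60/50 = 1.2 visits) | 10×1.2² = 14.4 | 0.333 − 0.240 = 0.093 | 1.03–1.07 | 5.3–5.8% |
| 46 | 9 single-visit people | 9 | 0.60 − 0.15 = 0.45 | 1.14–1.32 | 6.6–8.7% |
| 46 | 9 at random (mean 60/46 = 1.30 visits) | 9×1.30² ≈ 15.3 | 0.60 − 0.255 = 0.345 | 1.10–1.24 | 6.2–7.9% |

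**One visit per person per period, 20% overlap.** There are no within-period repeats, so V = 1 − 0.2ρ = 0.94 to 0.86. The error rate is 4.3% to 3.5%.

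**Cancellation.** Take six people with two visits in each period (different people in the two periods) and twelve others with one visit in each. Then Σa² = 6×4 + 48 = 72 and 72/60 − 1 = 0.2. The overlap term is 12/60 = 0.2, so V = 1 and the error rate is 5.0%.

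Simulated t-tests (40,000 per setting) for the no-overlap, single-visit-overlap and one-visit cases agreed with the formula to within half a percentage point.

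**Power with first visits only.** Power = Φ(δ/√(2/n) − 1.96), taking the people in the two periods as distinct.

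| People per period | δ = 0.51 SD | δ = 1 SD (plan's example) |
|---|---|---|
| 60 | 80% | 99.98% |
| 54 | 76% | 99.94% |
| 48 | 71% | 99.84% |
| 46 | 69% | 99.77% |

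**The case against.** The strongest reply is that the plan speaks of patients throughout, including in the inclusion rule and the sample-size section, and that section 6 promises a de-identified serial number for patients' data. On that reading each person enters once per period, and the inflation from repeat visits disappears. This is fair. A reader might infer that the plan tests visits as though each were a different person, but the text does not say so. Per-episode outcomes and a sample size drawn from admission rates make visits a plausible unit, not a stated one. The reply does not settle the matter. Entering each person once still leaves people who appear in both periods, and then the unpaired test is the wrong one. Nor does a serial number, as described, have to follow a person from one period to the next.

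A second reply is that every repeat rate and correlation here is assumed, the effect is modest, and it can vanish. That stands. A reader might infer that the error rate is always inflated. The calculations do not support this, since it can also lie below 5%.

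A reader might also infer that a return after a poor decision adds a new case and so dilutes the violence and reversal rates. The documents do not support that. Admissions are the intended denominator for reversal. Returns can occur in the pre-period too, so a bias would need different return patterns in the two periods. Nothing says that returning patients are less violent than others. The point is not relied on here.

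**Conclusion.** The concern holds in a limited form. The unit of analysis is undefined, nothing is said about repeat attenders, and the prespecified tests are not valid if a person recurs within a period (when visits are counted) or across periods (on either reading). The direction of the error cannot be known from the documents. Under the stated assumptions the true two-sided error rate ranges from about 3.5% to 10%. The upper end needs 46 people behind 60 visits, a correlation of 0.7 and no overlap. The lower end needs one visit per person per period, 20% overlap and a correlation of 0.7. If few people recur, or the two effects offset each other, the rate is close to 5%. This is a modest weakness that a better method removes cheaply, and it does not show that any result would be wrong.

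**What to change.** - **Patient Population (section 4):** state that the main analysis uses each person's first qualifying visit in each period.
- **Statistical Analyses (section 4):** replace the unpaired t-test and chi-square test by regression on period (linear or logistic, according to the outcome), with standard errors clustered by person. Apply the same clustering to any covariate-adjusted model.
- **Supporting analysis:** repeat the comparison on all qualifying visits with the same clustering. First visits alone leave returns out of sight, so also report how many people attended more than once, within each period and across both.
- **Data collection:** keep one de-identified number per person across both periods. Set this up at collection, because it may be hard to rebuild afterwards.

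The cost is some wording, one linking field and some precision. With 48 to 54 people left per period, power for a 0.51 SD effect falls from about 80% to 71-76% (about 69% at 46 people). The plan's own example of 1 h with SD 1 h stays above 99%. Part of this loss is only apparent: with six people per period attending twice and a correlation of 0.5, V = 1.10. All 60 visits, properly analysed, would then give Φ(0.5115/√(1.10×2/60) − 1.96) ≈ 76%, much the same as 54 first visits.
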